### **3.2.1 Equivalence between test and reference product**

At least 261 subjects in Test Drug and 261 subjects in Reference Drug group will be required to show bioequivalence between Test and Reference product with 90% power and 5% level of significance assuming the following estimates:

- 1) 5% difference between Test and Reference of mean change in WOMAC score
- 2) 75 % inter subject coefficient of variation for Reference in WOMAC Score
- 3) Equivalence margin of 80.00-125.00%

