12.6 Sample Size Considerations

Equivalence between test and reference product⁷

At least 261 subjects in Test Drug and 261 subjects in Reference product will be required to show bioequivalence between Test and Reference product with 90% power and 5% level of significance assuming below estimates:

- 1) 5% difference between Test and Reference of mean change in WOMAC score
- 2) 75 % Inter subject coefficient of variation for Reference in WOMAC Score
- 3) Equivalence margin of 80.00-125.00%

Superiority of test and reference product over placebo

At least 363 number of subjects will be required in each arm to prove the superiority of test/ reference product and placebo product with 90% power and 5% level of significance.

Considering 10% dropout rate, around 1212 subjects would be required to enroll for the study. All Subjects would be randomize in 1:1:1 treatment allocation.

Conclusion: Since the study has two hypotheses viz Equivalence and Superiority, we have chosen the highest sample size.

Test Product: 404 subjects.

Reference Product: 404 subjects

Placebo: 404 subjects

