**Figure 1 Study Design**

### 3.2 Sample Size

The study protocol, MYL-1601N-3002, is designed to demonstrate the Bioequivalence of Diclofenac Sodium Gel to Voltaren® Gel and the superiority of Diclofenac Sodium Gel and/or Voltaren® Gel over Placebo by using a clinical endpoint in patients with Osteoarthritis (OA) of the Knee. The clinical endpoint under consideration is the change from baseline Western Ontario and McMaster Universities Osteoarthritis Index (WOMAC) Likert (version 3.1) pain score. The framework under consideration and the sample size requirements were fine-tuned to satisfy the objectives of bioequivalence of test drug with the reference drug as well as superiority of the test drug to placebo. The sample size estimation is done to ensure 90% statistical power to test two hypotheses of bioequivalence and superiority, the hypotheses are briefly described below:

1. Null Hypothesis (Equivalence) is that the ratio of mean change from baseline in WOMAC Likert pain score between test and reference drug is less than or equal to 0.80 or greater than or equal to 1.25 Vs. the alternative hypothesis of ratio of mean change

from baseline in WOMAC Likert pain score between test and reference drug lies within the limits of 0.80 to 1.25, where the equivalence limit of 0.80 to 1.25 is adapted.

2. Null Hypothesis (Superiority): The mean change from baseline WOMAC Likert pain score of test or reference drug is greater than or equal to Placebo vs the alternative hypothesis of mean change from baseline WOMAC Likert pain score of test or reference drug is less than the placebo group.

To meet the requirement for the two hypotheses, three tests need to be performed to meet overall objectives:

- 1) Bioequivalence between Diclofenac Sodium Gel and Voltaren®
- 2) Superiority of Diclofenac Sodium Gel over Placebo
- 3) Superiority of Voltaren® over Placebo

Sample size calculations are performed under the following assumptions:

1. Mean ( $\pm$  Standard Deviation) reduction from baseline in WOMAC pain score is 5.85 ( $\pm 4.23$ ) for both active treatments.
2. Mean ( $\pm$  Standard Deviation) reduction from baseline in WOMAC pain score is 4.68 ( $\pm 4.89$ ) for placebo.

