### **3.2.2 Superiority of test and reference product over placebo**

At least 363 subjects will be required in each arm to prove the superiority of test/reference drug to placebo with 90% power and 5% level of significance.

Considering 10% dropout rate, around 1212 subjects will be required to enroll in the study. All subjects will be randomized in 1:1:1 ratio.

Overall, to satisfy both hypotheses of equivalence and superiority, the highest sample size will be used in the study: 1212 subjects equally randomized to Test, Reference and Placebo treatments:

1. Diclofenac Sodium Gel: 404 subjects.

2. Voltaren® Gel : 404 subjects
3. Placebo: 404 subjects

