#### **5. HYPOTHESES TESTING**

##### **Hypothesis of Equivalence (Primary Endpoint)**

The null hypothesis to be tested is that the ratio of mean change from baseline in WOMAC Likert pain score between test and reference drug is less than or equal to 0.80 or greater than or equal to 1.25 vs the alternative hypothesis that this ratio is within the interval from 0.80 to 1.25:

$H_0: \mu_T / \mu_R \leq \theta_1$  or  $\mu_T / \mu_R \geq \theta_2$  versus  $H_A: \theta_1 < \mu_T / \mu_R < \theta_2$

Where  $\mu_T$  = mean of test treatment, and  $\mu_R$  = mean of reference treatment

Typically,  $H_0$  will be rejected with a type I error  $\alpha = 0.05$  (two 1-sided tests), if the 90% confidence interval for the ratio of means between test and reference products ( $\mu_T / \mu_R$ ) is contained within the interval  $[\theta_1, \theta_2]$ , where  $\theta_1 = 0.80$  and  $\theta_2 = 1.25$ .

A two-sided, 90% confidence interval on the test/reference ratio for mean change from baseline to Week 4 in total WOMAC Pain Subscale score for the Target Knee will be constructed using Fieller's method. The estimates of treatment means and standard errors will be obtained from Analysis of Covariance (ANCOVA) of the Test and Reference results, using a statistical model containing fixed effects for treatment and center and baseline WOMAC Pain Subscale score as covariate.

Bioequivalence will be established if the 90% confidence interval for the ratio of test/reference means is contained within the interval  $[0.80, 1.25]$  for Per Protocol population.

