## **6.6 Per Protocol Population (PP Population)**

The Per Protocol (PP) population includes all mITT subjects who:

- met all inclusion/exclusion criteria
- apply 75% to 125% (both inclusive) of the scheduled applications of the assigned product
- return for the 4 week evaluation of WOMAC Pain Subscale score within the visit window (+/- 4 days; i.e., study Day 24-32) or discontinue from the study due to treatment failure (included as treatment failures)
- have no major protocol deviations impacting the primary efficacy outcome measure.

These major protocol deviations are described in [section 7.9](#). The list of protocol deviations which lead to exclusion of subjects from the PP population will be finalized at the Blind Data Review (BDR) meeting to be held prior to database lock.

This population will be used for testing the clinical equivalence.

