## 7.10 Handling of Missing Data

For demographic and baseline characteristics, each variable will be analyzed using all available data. Subjects with missing data will be excluded only from analyses for which data are not

available. For efficacy analysis, patients who discontinued the study early will be included in the ITT and mITT analysis with LOCF approach; subjects who discontinue the study due to lack of treatment effect will also be included in the PP analysis with LOCF approach.

For WOMAC pain total score, the following imputation method will be used for handling missing values. If one item is missing, the missing value will be imputed by averaging remaining 4 items and total score will be calculated using sum of 5 items. If more than one items are missing, then the total pain score will be assigned to missing value at that visit. The LOCF method will be used for endpoint analysis if Visit 5 value is missing.

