#### **7.11.2.1 Analysis of clinical equivalence of test and reference treatments**

To show the clinical equivalence, estimates of LS mean change from baseline to Week 4 in the WOMAC Pain Subscale score will be calculated for the test and reference treatment, and then the 90% CI for the LS mean ratio will be constructed using Fieller's method. Bioequivalence will be established if the 90% confidence interval for the ratio of test/reference LS means is contained within the interval [0.80, 1.25].

To this end, first an ANCOVA model will be fit with change from baseline to Week 4 in the WOMAC Pain Subscale score as outcome, baseline WOMAC Pain Subscale score as covariate and treatment, center and treatment-by-center interaction as factors on the data from test and reference treatments only (excluding Placebo subjects):

$$Y_{ijk} = b + a \cdot B_{ijk} + T_i + C_j + TCI_{ij} + \varepsilon_{ijk}$$

Where

- $Y_{ijk}$  is the change from baseline to Week 4 in WOMAC Pain Subscale score for the  $k$ th subject in the  $j$ th center with  $i$ th treatment
- $b$  is model intercept
- $B_{ijk}$  is the baseline WOMAC Pain Subscale score for the  $k$ th subject in the  $j$ th center with  $i$ th treatment
- $a$  is the model parameter associated with baseline WOMAC Pain Subscale score
- $T_i$  is the effect of the  $i$ th treatment
- $C_j$  is the effect of the  $j$ th center
- $TCI_{ij}$  is the interaction effect of the  $i$ th treatment and the  $j$ th center
- $\varepsilon_{ijk}$  is the random error (normally distributed with zero expected value)

If the treatment-by-center interaction factor is not significant at the 0.05 level, the model will be rerun without the interaction term. Treatment LS means and standard errors will be estimated from this model. Then Fieller's formula will be applied; covariance between treatment means will be assumed to be 0. See [appendix 11.2](#) for complete description of Fieller's formula.

Equivalence will be illustrated graphically by a plot including a vertical line corresponding to the 90% CI around the Test/Reference ratio with the ratio itself indicated by a dot with reference lines for 80% and 125%.

Analysis of bioequivalence will be performed primarily on the Per Protocol population, and additionally on the ITT and mITT populations as a sensitivity analysis.

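### The 261 per arm stated for equivalence gives about 80% to 85% power, not 90%, under the planned Fieller test; enrolment of 404 per arm is unaffected

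*SAP*

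**What the plan says.** Both documents give the same equivalence requirement. SAP 3.2.1: "At least 261 subjects in Test Drug and 261 subjects in Reference Drug group will be required to show bioequivalence". Protocol 12.6: "At least 261 subjects in Test Drug and 261 subjects in Reference product will be required". Each attaches 90% power and a 5% level to it, with three inputs: a 5% difference between Test and Reference in mean change, a 75% between-subject CV for Reference, and limits of 80% to 125%. Neither names the formula, the scale, or the direction of the 5% difference.

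The SAP does name the analysis. Section 5 says the interval "will be constructed using Fieller's method", and 7.11.2.1 repeats that "the 90% CI for the LS mean ratio will be constructed using Fieller's method". The LS means come from an ANCOVA of the untransformed change from baseline, with baseline score and center in the model, and their covariance is taken as 0. No log transformation is planned.

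SAP 3.2 also gives a mean and SD: the "reduction from baseline in WOMAC pain score is 5.85" with SD 4.23, for both active arms. Enrolment follows from the larger superiority requirement of 363 per arm: "Considering 10% dropout rate, around 1212 subjects will be required to enroll in the study", that is 404 per arm.

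Equivalence is tested in the per-protocol (PP) population. Besides compliance and visit-window conditions, SAP 6.6 requires that subjects "have no major protocol deviations impacting the primary efficacy outcome measure". Subjects who stop early "due to lack of treatment effect will also be included in the PP analysis with LOCF approach" (SAP 7.10).

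**The concern.** A sample size is tied to the test it was computed for. A log-scale calculation uses the log SD and log distances to the limits. The Fieller interval uses the raw SD relative to the reference mean. At a CV of 75% the two differ materially. A log scale would also be awkward for this endpoint, because a change score can be zero or negative. If changes were normal with mean 5.85 and SD 4.23 (an assumption), about 8% would be at or below zero.

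Equivalence is a primary objective, and the study succeeds only if it and both superiority tests succeed (SAP 7.1.2). Read literally, 261 says that PP could fall from 404 to 261 per arm, a 35% loss, with 90% power intact. If that is wrong, the documents overstate the room for PP exclusions, which go beyond the 10% dropout allowance. Neither document gives an expected PP rate.

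**Working it through.** **Inputs.** n = 261 per arm, 5% difference, CV 0.75, limits 0.80 and 1.25 (SAP 3.2.1, Protocol 12.6); one-sided level 0.05 for each of two tests (Protocol 12.3.1, SAP 5); Fieller on untransformed means with zero covariance (SAP 7.11.2.1). Assumed: the same SD in both active arms, as in SAP 3.2, and no covariate gain.

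**1. Reproducing 261.** Log-scale two one-sided tests, parallel groups, ratio 0.95:
- log SD = sqrt(ln(1 + 0.75²)) = 0.668
- SE = 0.668 × sqrt(2/261) = 0.0585
- distance to the nearer limit = ln(0.95/0.80) = 0.1719, or 2.94 SE

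Exact t-based power is 90.03% at 261 and 89.93% at 260, so 261 is the first n to reach 90%. The documents do not name this method; it is inferred from the exact match. At ratio 1.05 the same method gives 254.

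**2. Power of the planned test at 261.** The 90% Fieller interval lies inside 0.80 to 1.25 when both linear contrasts, T − 0.80R and 1.25R − T, are significantly above 0. Set the reference mean to 1, so SD = 0.75. The critical t on 520 df is 1.648.
- SE(T − 0.80R) = 0.75 × sqrt((1 + 0.64)/261) = 0.0595
- SE(1.25R − T) = 0.75 × sqrt((1 + 1.5625)/261) = 0.0743

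Ratio 0.95:
- lower limit: 0.15/0.0595 = 2.523, so Φ(2.523 − 1.648) = 0.809
- upper limit: 0.30/0.0743 = 4.037, so Φ(4.037 − 1.648) = 0.992
- joint power **80.1%**

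Ratio 1.05:
- lower limit: 0.25/0.0595 = 4.205, giving 0.995
- upper limit: 0.20/0.0743 = 2.691, giving 0.852
- joint power **84.6%**

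Simulating the Fieller interval itself (1,000,000 replicates) gives 80.1% and 84.6%.

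**3. Size needed, and sensitivity to the inputs.**

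| CV | Ratio | Power at 261 | n per arm for 90% | Power at 363 |
|---|---|---|---|---|
| 75% | 0.95 | 80.1% | 354 | 90.7% |
| 75% | 1.05 | 84.6% | 312 | 93.6% |
| 72.3% (= 4.23/5.85) | 0.95 | 82.8% | 329 | 92.5% |
| 72.3% | 1.05 | 87.0% | 290 | 95.0% |
| 75% | 1.00 | 91.4% | 251 | 98.0% |

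With equal CVs instead of equal SDs, at CV 75%, power at 261 is 82.3% (0.95) or 83.2% (1.05), and 333 or 324 per arm are needed.

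**4. Covariate gain that would rescue 261.** The residual variance would have to fall by 26% (0.95) or 16% (1.05) at CV 75%, or by 21% or 10% at CV 72.3%. At ratio 0.95 and CV 75%, reductions of 10%, 20% and 26% lower 354 to 318, 283 and 262.

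**5. Enrolment and PP size.** 354/0.9 = 393.3, so 394 per arm, below 404. At ratio 0.95 and CV 75%, PP loss from 404 can reach 1 − 354/404 = 12% before power drops under 90%. At 323 per arm (20% loss) power is 87%; at 303 (25% loss) it is 85%.

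**The case against.** The strongest reply is that nothing in the design depends on 261. Superiority fixes 363 evaluable and 404 enrolled per arm, and even the largest Fieller requirement found here, 354, is below 363. That stands, and it limits the point to a wrong power statement.

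Second, 261 is not a slip in arithmetic, since it reproduces exactly. Also true: the fault is that the sizing method, which is itself inferred, does not match the analysis method. The shortfall does not depend on where 261 came from.

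Third, the planned test is an ANCOVA, and a large enough covariate gain would bring 261 back to 90%. The documents state no gain and do not say whether the 75% is raw or residual, so the claimed 90% cannot rest on one.

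Fourth, the replacement figure depends on choices the documents leave open: direction, Test-arm variance and CV. Before any covariate gain, the variants with a 5% difference run from 290 to 354. This is a fair caution against quoting 354 without its assumptions. But every one of those variants leaves 261 below 90%. SAP 3.2 supports equal SDs by giving one SD for both active arms.

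Finally, SAP 3.2 assumes equal active means, under which 261 gives 91.4%. SAP 3.2.1, however, sets a 5% difference for the equivalence calculation.

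**Conclusion.** The concern holds. On the stated 5% difference and 75% CV, the planned Fieller test has 80.1% (ratio 0.95) to 84.6% (ratio 1.05) power at 261 per arm, and needs 354 or 312 per arm for 90%. These figures assume equal SDs in the two active arms and no variance reduction from the ANCOVA. Equal CVs keep power at 261 within the same range, and a CV of 72.3% raises it to 83% to 87%.

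The trial is large enough if PP loss stays close to the 10% allowance: power at 363 per arm is at least 90.7%. Beyond that the decline is gradual, and treatment failures retained by LOCF limit the loss. What fails is the use of 261 as the size at which the primary equivalence test still has 90% power.

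**What to change.** In Protocol 12.6 and SAP 3.2.1:
- Replace 261 with the requirement for the Fieller test. With equal SDs, CV 75% and no covariate gain, this is 354 per arm in PP at ratio 0.95, or 312 at 1.05.
- Name the method, the direction of the 5% difference and the Test-arm variance assumption.
- State whether the CV is raw or residual after ANCOVA, and reconcile 75% with 4.23/5.85 = 72.3%. If a covariate gain is assumed, give its size.
- Report equivalence power at the PP size expected after all PP exclusions.

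Keep 404 per arm. The cost is restated figures and a short statement of method in two documents, plus the approvals that Protocol 14.6 requires for a protocol revision. No patients or visits are added.

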### **3.2.2 Superiority of test and reference product over placebo**

At least 363 subjects will be required in each arm to prove the superiority of test/reference drug to placebo with 90% power and 5% level of significance.

Considering 10% dropout rate, around 1212 subjects will be required to enroll in the study. All subjects will be randomized in 1:1:1 ratio.

Overall, to satisfy both hypotheses of equivalence and superiority, the highest sample size will be used in the study: 1212 subjects equally randomized to Test, Reference and Placebo treatments:

1. Diclofenac Sodium Gel: 404 subjects.

2. Voltaren® Gel : 404 subjects
3. Placebo: 404 subjects

### **3.3 Randomization and Unblinding Procedures**

A computerized randomization will be generated by an independent statistician (not involved in the packaging and labelling of the study medication).

Subjects will be randomly assigned in 1:1:1 ratio to three groups. Treatment allocation can be Mylan's Diclofenac Sodium Topical Gel 1%, Voltaren® Gel 1% (Reference Listed Drug), or Placebo. A balanced randomization schedule will be generated using SAS® software (Version: 9.3 or higher; SAS Institute Inc., USA). The randomization code will be held by an independent statistician throughout the conduct of the study in order to minimize bias.

A sealed copy of the randomization code for each kit provided under separate cover inside the block will be retained at investigational center. It should be available to FDA investigators at the time of center inspection to allow for verification of the treatment identity of each subject.

Placebo run-in period will be single blinded, in which subjects will not be aware of the treatment given.

Treatment period will be double blinded, in which all the investigators, subjects, center staff, CRO team, study monitors, laboratory personnel and/or other designated individuals will be blinded to the medication codes. The formulation of test, reference and placebo investigational products will be identical in appearance to make any difference in treatment less obvious to the subjects and to maintain adequate blinding of evaluators.

Planned unblinding will occur after the database lock.

Unplanned unblinding (prior to database lock) will be performed by a designated person in case of SAE or other significant events. Mylan Product Safety and Risk Management (PSRM) can unblind the treatment assignment for any subject with a SAE which qualifies for the unblinding based on country specific regulatory requirements.

The event of unplanned unblinding prior to database lock shall be documented in the source notes. Reasons for treatment unplanned unblinding must be clearly explained and justified in the

eCRF. The date on which the code was broken together with the identity of the person responsible must also be documented.

If a subject's treatment assignment is unblinded prior to database lock for any reason then the subject should be withdrawn from the study.

#### **4. STUDY ENDPOINTS/OUTCOMES**

##### **Primary Efficacy Endpoint**

The primary efficacy endpoint is the change from baseline to Week 4 in total WOMAC Pain Subscale score for the Target Knee.

##### **Secondary Efficacy Endpoints**

The secondary efficacy endpoints are:

- The change from baseline to Week 2 in total WOMAC Pain Subscale score for the Target Knee.
- The change from baseline to Week 4 in total WOMAC Pain Subscale score for the Target Knee for the subgroup of subjects whose baseline WOMAC pain score is less than or equal to 10.
- The change from baseline to Week 4 in POM VAS score for the Target Knee.
- Number of days of acetaminophen (paracetamol) consumption during the trial.
- Average daily dose of acetaminophen (paracetamol) during the trial

##### **Safety Endpoints**

1. The incidence of treatment-emergent adverse events
2. Application site reaction evaluation

#### **5. HYPOTHESES TESTING**

##### **Hypothesis of Equivalence (Primary Endpoint)**

The null hypothesis to be tested is that the ratio of mean change from baseline in WOMAC Likert pain score between test and reference drug is less than or equal to 0.80 or greater than or equal to 1.25 vs the alternative hypothesis that this ratio is within the interval from 0.80 to 1.25:

$H_0: \mu_T / \mu_R \leq \theta_1$  or  $\mu_T / \mu_R \geq \theta_2$  versus  $H_A: \theta_1 < \mu_T / \mu_R < \theta_2$

Where  $\mu_T$  = mean of test treatment, and  $\mu_R$  = mean of reference treatment

Typically,  $H_0$  will be rejected with a type I error  $\alpha = 0.05$  (two 1-sided tests), if the 90% confidence interval for the ratio of means between test and reference products ( $\mu_T / \mu_R$ ) is contained within the interval  $[\theta_1, \theta_2]$ , where  $\theta_1 = 0.80$  and  $\theta_2 = 1.25$ .

A two-sided, 90% confidence interval on the test/reference ratio for mean change from baseline to Week 4 in total WOMAC Pain Subscale score for the Target Knee will be constructed using Fieller's method. The estimates of treatment means and standard errors will be obtained from Analysis of Covariance (ANCOVA) of the Test and Reference results, using a statistical model containing fixed effects for treatment and center and baseline WOMAC Pain Subscale score as covariate.

Bioequivalence will be established if the 90% confidence interval for the ratio of test/reference means is contained within the interval  $[0.80, 1.25]$  for Per Protocol population.

### **Hypothesis of Superiority (Primary Endpoint)**

The null hypothesis to be tested is that there is no difference in the mean change from baseline to Week 4 in total WOMAC Pain Subscale score for the Target Knee between the active treatment and the Placebo treatment vs the alternative hypothesis that the reduction in the WOMAC Pain Subscale score is greater for both active treatments than for placebo:

$H_0: \mu_T = \mu_P$  and  $\mu_R = \mu_P$  versus  $H_A: \mu_T < \mu_P$  and  $\mu_R < \mu_P$

Where  $\mu_T$  = mean of test treatment,  $\mu_R$  = mean of reference treatment,  $\mu_P$  = mean of Placebo treatment.

The hypothesis testing will be performed separately for the Test treatment versus the Placebo treatment and for the Reference treatment versus the Placebo treatment using Analysis of Covariance (ANCOVA) with a statistical model containing fixed effects for treatment and center and baseline WOMAC Pain Subscale score as covariate.

Superiority will be established if the mean change from baseline for each active treatment is less than, and statistically significantly different from ( $p < 0.05$ ), that for the Placebo using the

modified intent-to-treat (mITT) population and with Last Observation Carried Forward (LOCF) approach.

